8.1. Definition of the primary end point and secondary end points

Primary outcome of the study will be clinical response as defined by >30% improvement from the baseline score of the Salpêtrière Retardation Rating Scales (SRRS). Moreover, gross motor behavior (actigraphy), fine motor function (finger tapping test), and hand gesture performance (TULIA) will be assessed at baseline and after the last TMS. Furthermore, we will investigate the efficacy of TMS on disorder specific symptoms; in patients with major depressive disorder, HAMD, MADRS and BDI, in patients with schizophrenia PANSS, SANS, CAINS and the Bush Francis Catatonia Rating Scales will be carried out before and after TMS. Statistical analysis will comprise ANOVAs of motor variables and stimulation mode as between subject variable. Clinical response will be defined as a 30% reduction of the SRRS scores. Frequency of response will be compared between groups using Chi²-Tests.

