8.2. Planned number of trial subjects with clearly stated justification (power analysis)

When we simulate a distribution of responders, in which two groups get 25% of the responders, the more effective group third group gets 40% and the most ineffective group only 10%, and compare this distribution to an equal distribution of 25% in each group, then the df is 3, noncentrality $\lambda = 14.22$, critical $X = 7.8$ and the effect size $\omega = 0.42$. Thus, we could expect a medium to large effect.

Applying a Chi²-Test with this effect size of $\omega = 0.42$, a significance level of $\alpha = 0.05$, a power of $1-\beta = 0.90$ and a df = 3, then the total required sample size would be 79 subjects. Therefore, each group has to contain at least 20 subjects.

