8.3. Description of the statistical methods foreseen and the planned intermediate assessments

Descriptive data analyses will be performed using Statistical Package for Social Sciences SPSS 17.0® (SPSS Inc., Chicago, IL, USA). In order to compare efficacy of the intervention arms, the primary outcome will be the frequency of patients

achieving response to psychomotor retardation (i.e. >30% improvement from SRRS baseline scores). This group statistic will be calculated using Chi²-Tests.

In order to investigate the effect of rTMS on the psychomotor performance of participants, we will analyze changes in motor variables within and between groups using repeated measures-ANOVAs. This way, we will test for time effects and effects of stimulation protocol. In case of unequal distribution of descriptive parameters between groups, these parameters will be entered as covariates to the repeated measures ANCOVA. Before performing ANOVAs, a normalizing transformation will be carried out if necessary.

The same procedure will be followed in case of the diagnose specific symptoms ratings (BDI, MADRS, Hamilton, PANSS, SANS, CAINS).

To control if a possible improvement of psychomotor performance after rTMS may be attributed to a general clinical response, we will use the analysis of covariance (ANCOVA) with psychomotor performance ratings (before and after TMS) as within subjects factor and changes in ratings of diagnose specific symptoms ratings as covariate.

At three major recruitment steps (25% of total sample, 50% and 75% respectively) we will calculate the primary analysis. If one group proves to have significantly poorer outcome than the others, we will stop this study arm.

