8.4. Planned significance level

Planned level of significance will be held as p<0.05.

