8.5. Handling of missing data, dropout cases

Only complete data records with assessments at two time points will be entered in the analyses. In case of dropout we will perform an intention-to treat (ITT) analysis applying the last-observation-carried-forward method (LOCF). In case of revocation of patients (KlinV, Art.9), data will be anonymized.

9. Study-specific safety precautions and responsibilities

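### The interim rule for stopping a poorer arm (Section 8.3) defines neither the comparison nor an interim level, so the chance of stopping an equally effective arm runs from about 1% to about 40% depending on how it is read

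*Combined protocol and SAP*

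**What the plan says.** The primary outcome is response, meaning more than 30% improvement on the SRRS. Section 8.1: "Frequency of response will be compared between groups using" chi-square tests. Section 8.3 adds the interim plan: "At three major recruitment steps (25% of total sample, 50% and 75% respectively) we will calculate the primary analysis". The action follows: "If one group proves to have significantly poorer outcome than the others, we will stop this study arm". Section 8.4 is one line: "Planned level of significance will be held as p<0.05". Section 8.2 sizes the trial with "a significance level of $\alpha = 0.05$, a power of $1-\beta = 0.90$ and a df = 3" and makes no allowance for interim looks. Its effect size comes from shares of responders, "in which two groups get 25% of the responders" and the other two 40% and 10%. It gives no response rates.

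No section names the test that shows one group to be poorer than the others, gives an interim level, says whether the rule covers the sham arm, or says what happens to a stopped arm's patients in the final test. Section 8.5 says "Only complete data records with assessments at two time points will be entered in the analyses", but that sentence restricts the data set because of dropout and does not address stopped arms.

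**The concern.** The rule decides which arms survive, yet it cannot be run as written. A four-group chi-square with 3 degrees of freedom can show that the arms differ, but not which one is poorer. A second comparison is needed, and it would have to be chosen with interim data in view. If 0.05 is used at each look, there are three looks at four arms with no adjustment.

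The first consequence is that an equally effective arm may be closed by chance. If the rule covers sham, a quarter of chance stops fall, by symmetry, on the only control. The second is that closing the lowest arm at its worst moment disturbs the final test, to an extent that depends on whether its data stay in. The first look is also too small for the planned test.

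**Working it through.** **The plan's own figure.** From Section 8.2, w = √[Σ(share − 0.25)²/0.25] = √[(0.15² + 0.15²)/0.25] = √0.18 = 0.424. The critical value at 3 df and 0.05 is 7.815, and 90% power needs noncentrality of about 14.17. N = 14.17/0.18 = 78.7, rounded up to 79; 79 × 0.18 = 14.22, with power 0.901. The stated 79 reproduces, as a single test at 0.05.

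**The looks.** With 80 patients and equal allocation, 25/50/75% is 20/40/60 patients, or 5/10/15 per arm. At the first look the expected counts per arm are 5p and 5(1−p). They sum to 5, so both are below 5 at any response rate p between 0 and 1.

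**Simulation with no true difference.** Assumptions: common response 20-50%; 5/10/15/20 per arm; complete outcomes at each look; Pearson chi-square at 0.05 at each look; the first trigger stops the lowest arm; at most one stop; the other arms recruit to 20. The last column is the error of the final four-arm test at 0.05 with the stopped arm's data kept.

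| Reading of the rule | Arm wrongly stopped | Final error, data kept |
|---|---|---|
| Worse than each other arm, pairwise | 0.7-2.6% | 4.7-5.6% |
| Four-group test and lowest against rest both significant | 3.3-8.2% | 4.9-6.5% |
| Four-group test alone, lowest arm stopped | 8.5-10.7% | 5.0-6.6% |
| Lowest against pooled rest alone | 10.8-22.1% | 4.5-6.9% |
| Worse than any one arm, pairwise | about 33-40% | 4.9-7.1% (response 30-50%) |

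Without stopping, the final error is 4.7-5.1%. Reallocating freed places or allowing more than one stop widens the range for the three middle readings to 4.4-7.0%. The top of the range is at 50% response; at 20% there is little or no inflation. If the stopped arm is left out of the final test, the error under these readings is about 2.5-3.9%, which is conservative.

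**Simulation with a true difference.** Shares convert to response rates as 4 × share × mean response. At an assumed mean of 50%: 4 × 0.10 × 50% = 20%, 4 × 0.25 × 50% = 50%, 4 × 0.40 × 50% = 80%. Means of 37.5% and 25% give 15/37.5/37.5/60% and 10/25/25/40%.

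| Mean response | Final power, no stopping | Worst arm stopped, each-other-arm reading | Worst arm stopped, three middle readings |
|---|---|---|---|
| 50% | 0.94 | 31% | 75-80% |
| 37.5% | 0.72 | 18% | 48-62% |
| 25% | 0.43 | 6% | 22-37% |

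At a mean of 50%, final power under the three middle readings is 0.88-0.93 with the stopped arm kept and 0.56-0.60 with it left out. Under the each-other-arm reading with data kept it stays at 0.94.

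**The case against.** The best defence is that the wording of Section 8.3 most literally means worse than each of the other arms. On that reading wrong stops are about 1-3%, the final error is 4.7-5.6% and power hardly moves, so there is almost no error problem. This stands as far as it goes. However, the plan does not commit to that reading, and other readings consistent with the text give rates more than ten times higher. Stopping a truly inferior arm is also the purpose of the rule, not a harm in itself.

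Three stronger readings are tempting, and the documents do not support them.

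- A reader might infer that four unadjusted tests raise the false-positive rate of the efficacy claim to 10.6-12.8%. That is the chance that at least one of the four four-group tests falls below 0.05 at an assumed response of 20-50%. Section 8.3 uses the interim looks only to stop a poorer arm and plans no early efficacy claim, so this is not the error of any claim the trial would make.
- A reader might take 0.05 at each look as stated. It is an inference from Section 8.4 giving no other level.
- A reader might report the fall in power to 0.56-0.60 as the effect of the rule. It applies only if a stopped arm's data are discarded, which no section says. Nor does Section 8.5 settle that they are kept.

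The simulation is also idealised. Looks are tied to recruitment, but response is measured after 15 daily sessions over 3 weeks, so fewer than 5/10/15 per arm may be evaluable at each look, and dropout is ignored.

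**Conclusion.** The point holds as a defect in the arm-stopping rule and should be fixed. The rule gives no comparison and no interim level, and its first look has only 5 patients per arm. With no true difference, the chance of closing an equally effective arm is about 1-3% on the strictest reading and about 33-40% on the loosest, with 3-8%, 9-11% and 11-22% between.

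Inflation of the final test is modest (4.4-7.0% under the three middle readings, against 4.7-5.1% without stopping) and appears mainly near 50% response. The plan's silence on a stopped arm's data matters more for power than for error.

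All the simulated figures rest on assumed response rates, 0.05 at each look, equal arms and complete outcomes.

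**What to change.** Amend Sections 8.3 and 8.4 as follows:

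1. At each interim, compare the arm with the lowest response with the pooled other arms by Fisher's exact test at a stated strict level.
2. Make no efficacy claim at an interim.
3. Keep a stopped arm's patients in the final four-arm chi-square at p<0.05. No reduction of the final level is needed.
4. State whether the rule applies to the sham arm.

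Two workable levels, simulated with no true difference at assumed responses of 10-50%:

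| Interim level | Arm wrongly stopped | Final error at 0.05 | Worst arm stopped (mean response 50/37.5/25%) |
|---|---|---|---|
| p<0.005 | about 1% at most | 3.9-5.3% | 41/18/2% |
| p<0.001 | at most 0.2% | 4.0-5.1% | 25/7/0.3% |

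The change needs no extra patients, and final power is essentially that of no stopping (0.94/0.72/0.43 at the three means). The cost is less arm-stopping: compare the last column with 31/18/6% under the each-other-arm reading and up to 80/62/37% under the lowest-against-rest reading. At the first look, an arm with 0 of 5 responders would be stopped only if the others had at least 12 of 15 (p<0.005) or 14 of 15 (p<0.001), against 9 of 15 with Fisher's test at 0.05. How much stopping to keep is the sponsor's choice, provided the comparison and level are fixed in advance.

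### The 90% power in 8.2 ignores the arm-stopping rule in 8.3, and the plan does not say whether a stopped arm's patients stay in the final test

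*Combined protocol and SAP*

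**What the plan says.** The primary outcome in 8.3 is binary: "the primary outcome will be the frequency of patients" who improve by more than 30% on the SRRS. On the test, 8.3 says: "This group statistic will be calculated using Chi²-Tests".

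Section 8.2 sizes the trial from an assumed split across the arms, "in which two groups get 25% of the responders, the more effective group third group gets 40% and the most ineffective group only 10" per cent. It then sets out to "compare this distribution to an equal distribution of 25% in each group". With df = 3, an effect size of 0.42, alpha 0.05 and power 0.90, "then the total required sample size would be 79 subjects", hence at least 20 per group.

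Section 8.3 repeats the primary analysis at three recruitment steps (25%, 50% and 75% of the sample) and states: "If one group proves to have significantly poorer outcome than the others, we will stop this study arm". On the significance level, 8.4 says only: "Planned level of significance will be held as p<0.05".

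The documents do not say:
- which comparison shows that an arm is poorer, or at what interim significance level;
- whether the freed places go to the other arms;
- whether the stopped arm's patients enter the final test;
- what response rate is expected in any arm.

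**The concern.** The power calculation and the interim rule describe different trials. In the 8.2 scenario the poorest arm supplies half of the planned effect, and the rule in 8.3 is aimed at that same arm. If the arm is stopped and then left out, the final test compares three arms that differ much less than the four used for planning. If its patients are kept, most of the power survives. The plan does not choose between the two, and 8.2 reports 90% as if no arm could be stopped. What is at stake is whether the stated power describes the trial that will be run.

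**Working it through.** **1. The plan's own figure.** Shares 0.25, 0.25, 0.40, 0.10 against 0.25 each (8.2):

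w² = Σ(p₁ − p₀)²/p₀ = (0 + 0 + 0.15² + 0.15²)/0.25 = 0.18, so w = 0.424.

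Noncentrality = 79 × 0.18 = 14.22. The critical value (df 3, 0.05) is 7.81. Power is 90.1% at N = 79 and 90.5% at N = 80. The figures in 8.2 reproduce. The poorest arm contributes 0.15²/0.25 = 0.09, half of 0.18.

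This is a goodness-of-fit calculation on how responders are spread over the arms, so strictly the 79 counts responders.

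**2. From shares to response rates.** The planned test compares response frequencies in a 4×2 table. With equal arms and overall response rate r, the shares imply arm rates 0.4r, r, r and 1.6r, so

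w² = ¼ × 2 × (0.6r)² / [r(1 − r)] = 0.18 × r/(1 − r).

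This equals 0.18 only at r = 0.50, which gives 20/50/50/80%. At r = 0.40, w² = 0.12. At r = 0.25, w² = 0.06 (w = 0.245). The 50% overall rate is therefore an assumption, but it is the one under which the 8.2 effect size carries over to the planned test.

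**3. Simulation with the rule.** There were 100,000 trials per setting, with looks at 20, 40 and 60 patients (5, 10 and 15 per arm) and nominal p<0.05 at each look. At most one arm was stopped, and it had to be the uniquely lowest. Two readings of the rule were run: the overall four-group Chi-square, and the lowest arm against the other three pooled. Power is over all trials, including those with no stop. The final test is df 2 when the stopped arm is excluded and df 3 when its patients are kept. Refilling means 80 patients in total.

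| Overall response | Rule | Arm stopped | Excluded, no refilling | Excluded, refilled | Kept | No looks |
|---|---|---|---|---|---|---|
| 50% | overall | 84.9% | 59.3% | 64.8% | 92.3% | 94.3% |
| 50% | lowest vs rest | 87.0% | 56.0% | 63.0% | 88.3% | 94.3% |
| 40% | overall | 64.6% | 45.5% | 48.5% | 74.1% | 77.5% |
| 40% | lowest vs rest | 72.8% | 39.2% | 43.4% | 66.9% | 77.5% |
| 25% | overall | 31.9% | 28.2% | 28.8% | 40.1% | 42.9% |
| 25% | lowest vs rest | 42.3% | 23.5% | 24.4% | 35.3% | 42.9% |

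The 94% without looks is simulated. The noncentral approximation for the same table gives 90.5%.

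**4. Other readings of the rule, at 20/50/50/80%.** An arm stops in 32% of trials if it must be worse than each other arm, 75% with a continuity-corrected lowest-versus-rest test, 80% with Fisher's test and 96% with lowest versus best. Over all readings, power is 55–78% with the arm excluded (with or without refilling) and 86–94% with its patients kept.

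**5. Why exclusion costs so much.** If the 20% arm goes, 50/50/80% remain, with mean 60%:

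w² = ⅓ × (0.1² + 0.1² + 0.2²)/(0.6 × 0.4) = 0.02/0.24 = 0.083, against 0.18 for four arms.

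The df 2 power is 50% at N = 60 and 63% at N = 80. The simulated power among trials that stopped an arm, 54–64%, is in line with this.

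**The case against.** **Silence is not exclusion.** A reader might infer that the plan discards a stopped arm's patients. It does not say so: 8.3 says only that the arm is stopped, and 8.5 deals with dropouts, not with closed arms. This stands, so the 56–65% is conditional. If the patients are kept, the loss from 94% is about 2 to 6 points.

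**The rates and the rule are assumed.** A reader might also infer that the plan's own scenario implies a stop in about 85% of trials. Section 8.2 gives shares of responders, not response rates, and 8.3 does not define the comparison. This stands too. The 85–87% needs a 50% overall response and one of two particular tests.

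**The interim look is itself the primary analysis.** If a stop counted as a positive result, about 96–97% of trials at 20/50/50/80% would show some significant difference, at an interim or at the end. The three-arm test also asks a different question, namely whether the remaining arms differ, so 94% against 56–65% is not a like-for-like loss. That much stands. But the plan does not say that a stop is a positive primary result. With equal arms, a false stop occurs in about 7–10% of trials under the overall test and 14–22% under lowest-versus-rest. Finding one arm poor also does not test the hypothesis in 3.3 that inhibitory stimulation over the SMA helps.

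**Stronger treatments do not weaken the remaining comparison.** A reader might infer that they do, because the rule then fires more often. The figures show the opposite: power with the arm excluded is about 23–29% at 25% overall response, 39–49% at 40%, 56–65% at 50% and 87–93% at 60%. Only the stopping frequency rises along with it.

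**Conclusion.** The point holds in conditional form. The 90% in 8.2 belongs to one fixed four-arm test and takes no account of the stopping rule in 8.3, and the handling of a stopped arm in the final test is left open.

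At assumed rates of 20/50/50/80%, that open choice moves final-test power between roughly 56–65% (arm left out) and 88–92% (patients kept) under the two main readings of the rule. At lower overall response every figure is lower but the order is the same: at 40%, about 39–49% excluded, 67–74% kept and 78% without looks; at 25%, about 23–29%, 35–40% and 43%. Even the mildest reading of the rule leaves at most 78% with the arm excluded at 50% overall response.

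The documents do not support saying that the trial will have 56–65% power, or that its own scenario fixes the stopping frequency. They support saying that the stated power is not that of the plan as written, and that the plan lacks the definitions needed to compute it.

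**What to change.** In 8.3:
- define the comparison and the significance level that trigger a stop;
- say whether freed places are refilled;
- add: *All patients randomised to a stopped arm remain in the final four-group test, with the critical value taken from a simulation that includes the stopping rule.*

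In 8.2, state the assumed response rate in each arm and restate the power from that simulation. The definitions must come first, because the simulation cannot be set up without them.

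The cost is a few sentences and a short simulation, with no extra patients. With stopped-arm patients kept and the ordinary critical value, the simulated type I error is about 5–7%, so the adjustment should be small. There are two downsides. The restated power will be slightly less favourable. The stopped arm's observed response rate is selected to be low and rests on few patients, so it should be labelled as such wherever it is reported.

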8.4. Planned significance level

Planned level of significance will be held as p<0.05.

8.5. Handling of missing data, dropout cases

Only complete data records with assessments at two time points will be entered in the analyses. In case of dropout we will perform an intention-to treat (ITT) analysis applying the last-observation-carried-forward method (LOCF). In case of revocation of patients (KlinV, Art.9), data will be anonymized.

9. Study-specific safety precautions and responsibilities

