3.2. Research Questions, study population

Research Questions

We aim to investigate the effect of TMS in various configurations on psychomotor retardation in patients diagnosed with MDD or schizophrenia. Diagnoses will be given following application of Mini-International Neuropsychiatric Interview (MINI)(Sheehan et al., 1998) and review of the complete cases files. The study consists of a single site four arm randomized, sham-controlled trial. In total, 80 patients will be randomly assigned to four groups (20 patients per group) receiving sessions of TMS of different stimulation parameters. Sham stimulation will be administered in one group. Regardless of the type and the frequency of TMS, the

stimulation protocol will consist of 15 daily sessions during a 3 week period. The four different stimulation conditions have been described above.

Outcome will be evaluated as improvement in gross motor behavior (actigraphy, SRRS), fine motor function (finger tapping test), and hand gesture performance (TULIA). In addition, changes may be demonstrated by the Hamilton Rating Scale for Depression (HAMD) (Hamilton, 1960), Montgomery Åsberg Depression Rating Scale (MADRS) (Montgomery and Asberg, 1979) Beck Depression Inventory (BDI) (Beck et al., 1961), Positive and Negative Syndrome Scales (PANSS) (Kay et al., 1987) and Scales for the Assessment of Negative Symptoms (SANS) (Andreasen, 1983), Clinical Assessment Interview for Negative Symptoms (CAINS) (Kring et al., 2013) and Bush Francis Catatonia Rating Scales (Bush et al., 1996). Clinical ratings will be assessed at baseline and after the last TMS session by a rater blinded to stimulation protocol. Statistical analysis will comprise ANOVAs of motor variables and stimulation mode as between subject variable. Clinical response will be defined as a 30% reduction of the SRRS scores. Frequency of response will be compared between groups using Chi²-Tests.

Study Population

80 in- and outpatients with schizophrenia or major depressive disorder according to DSM-5 displaying reduced levels of motor activity. Diagnoses will be given following application of MINI and review of the complete cases files.

Age: 18-65

Right-handed

Races: all ethnic groups

Gender: male and female. Pregnant patients will be eliminated.

Patients must have normal or corrected-to-normal vision and hearing.

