4.1. Targeted primary end point and secondary end points (effectiveness and safety parameters)

Main objective is the effect of TMS on psychomotor retardation (PR) in patients with major depressive disorder or schizophrenia. Primary outcome marker will be the change in psychomotor performance as assessed by Salpêtrière Retardation Rating Scales (SRRS). Clinical response will be defined as a 30% reduction of the SRRS baseline scores.

Secondary targets will be the effect of TMS on other motor parameters and on specific symptoms e.g. depressive or negative symptoms.

Efficacy parameters: TMS parameters may be of critical role determining the effect of the applied TMS on motor symptoms.

Safety parameters: As specific safety factors in relation to TMS, patients with 1. past history of epilepsy, or 2. other increased neuronal activity in Electroencephalography (EEG), 3. MRI contraindications and 4. substance misuse will be excluded. EEG recordings will be held for all patients before the beginning of TMS. Patients will be screened every 5 sessions with SRRS and actigraphy. In case of moderate deterioration of motor performance (30% change of initial ratings of SRRS or/and actigraphy) or adverse reactions during the TMS protocol, patients will be excluded from further participation in the study. .

4.2. Specification of the parameter that is of primary interest and other parameters that will be assessed as additional, secondary end points.

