6.1. Effectiveness parameters: measuring methods and reference dates

The efficacy of TMS sessions will be evaluated primarily as improvement in SRRS baseline score after treatment. Furthermore, we investigate the effect of TMS on gross motor behavior (SRRS, actigraphy), fine motor function (finger tapping test), and hand gesture performance (TULIA). To this purpose, clinical ratings will be assessed twice, at baseline and after the last TMS **session**. Furthermore, changes may be demonstrated by the scales assessing the disorder specific symptoms; in patients with major depressive disorder, HAMD, MADRS and BDI, in patients with schizophrenia PANSS, SANS, CAINS and the Bush Francis Catatonia Rating Scales. Statistical analysis will comprise repeated measures ANOVAs of motor variables and stimulation mode as between subject variable. Clinical response will be defined as a 30% reduction of the SRRS scores.

7. Assessment of safety

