7.1. Safety parameters: measuring methods and times

Specific safety parameters for TMS include: past history of epilepsy, pregnancy, other increased neuronal activity in Electroencephalography (EEG), MRI contraindications and substance misuse other than nicotine. Female patients will take a urine pregnancy test before the beginning of the TMS sessions and they will be required to use contraceptive methods during the **study** in order to enroll in the study. In case of a suspicion of a pregnancy during the **study** despite the use of contraceptives a urine test will be taken. These parameters will be observed and are explicit exclusion criteria. EEGs of all patients will be recorded before the beginning of TMS. Patients displaying abnormal EEG findings will be excluded. The rest of above mentioned parameters will be as well observed and are explicit exclusion criteria. After every 5 sessions, assessments of gross motor behaviour (SRRS,

actigraphy) will be repeated. In case of moderate deterioration of motor performance (30% change of initial ratings) patients will be excluded from the **study**.

7.2. Guarantee of follow-up examination of patients in case of adverse reactions.

The study will be carried out according to the protocol. In case of serious adverse events, which may be connected to the TMS **stimulation** or any relevant assessments (Art.42, KlinV), the Ethics Committee will be as soon as possible informed by the sponsor. Serious adverse events may include seizures or exacerbation of psychiatric symptoms. In such cases the TMS sessions will be immediately stopped and the patient will be excluded from the study. A MRI examination will be held and any necessary additional medical consultations will be arranged.

8. Statistics

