9.2. If appropriate: exit examination in case of dropout

At the end of every week of the **TMS stimulation**, assessments of gross motor behaviour (SRRS, actigraphy) will be repeated. In case of moderate deterioration of motor performance (30% change of initial ratings), patients will be excluded from the **study**. In case of seizures or persisting headaches a Magnetic Resonance Imaging Examination will be held for diagnostic purposes.

10. Duties of the investigator

10.1. Confirmation that the conduct of the study will be in accordance with the GCP protocol, the current legal regulations and rights.

Hereby investigators confirm that they have knowledge of the GCP protocol, according to which the study will be carried out. All current legal regulations and rights will be additionally taken into account.

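### Section 8.5 gives two conflicting rules for dropouts and does not say which one is primary for the responder Chi² test and its three interim repeats

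*Combined protocol and SAP*

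**What the plan says.** Section 8.5 contains two rules, one after the other. The first is "Only complete data records with assessments at two time points will be entered in the analyses". The second is "In case of dropout we will perform an intention-to treat (ITT) analysis applying the last-observation-carried-forward method (LOCF"). Neither is labelled primary, supportive or sensitivity.

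The two time points can be identified from elsewhere. Section 6.1 says "clinical ratings will be assessed twice, at baseline and after the last TMS" session, and section 3.2 agrees: "Clinical ratings will be assessed at baseline and after the last TMS session by a rater blinded to stimulation protocol".

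Sections 8.1 and 8.3 make response (more than 30% SRRS improvement from baseline) the primary outcome and compare its frequency across the four arms by Chi², without naming an analysis set. Section 8.3 adds: "At three major recruitment steps (25% of total sample, 50% and 75% respectively) we will calculate the primary analysis". An arm with significantly poorer outcome is then stopped.

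Patients can be taken out during treatment because of their motor ratings. Section 4.1 applies to "30% change of initial ratings of SRRS or/and actigraphy) or adverse reactions during the TMS protocol, patients will be excluded from further participation". Section 7.1 says "In case of moderate deterioration of motor performance (30% change of initial ratings) patients will be excluded from the" study, and section 9.2 says the same. Section 9.1 instead says that such patients stop the stimulation. SRRS and actigraphy are repeated after every 5 sessions (sections 4.3, 7.1 and 9.1).

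**The concern.** A patient who leaves before the last session has no rating at the second time point. The first sentence of section 8.5 shuts that patient out, and the second keeps the patient in. The denominator of the primary response rate is therefore not fixed in advance.

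In this trial the missing data are partly produced by the outcome. A patient removed because the SRRS has worsened is a known non-responder. Under the complete-record sentence that patient disappears from the denominator. Under LOCF the last SRRS is worse than baseline, so the patient counts as a non-responder.

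Two things are at stake:

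- The choice between the rules could be made after the results are known. This risk exists even if removal is equal across arms.
- If the complete-record rule is used and removal differs by arm, an arm that makes patients worse looks better than it is, both in the final test and at the looks that decide whether an arm stops.

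**Working it through.** **1. The plan's own figure.** Section 8.2 compares responder shares of 25/25/40/10% with 25% each.

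- w² = Σ(p − 0.25)²/0.25 = (0.15² + 0.15²)/0.25 = 0.18, so w = 0.424.
- With N = 79, λ = 79 × 0.18 = 14.22. The critical value for 3 df is 7.815 and power is 90.1%. The stated 79 is reproduced.
- Planned enrolment is 4 × 20 = 80 (power 90.5%), one patient more than required. On the same model, an assumed 10% dropout with complete records only leaves 72 patients: λ = 72 × 0.18 = 12.96, power 87.0%.

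Whether that power model suits the planned test is a separate matter. Steps 2 to 5 use the planned test itself: Pearson Chi², 3 df, 20 per arm.

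**2. Can the rule change the verdict?** X² = Σ nᵢ(pᵢ − p̄)² / [p̄(1 − p̄)], with hypothetical counts.

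- All randomised, responders 8/8/13/4 of 20: p̄ = 33/80 = 0.4125; X² = 2.0375/0.2423 = 8.41; p = 0.038.
- The same responders, with two non-responders of the weakest arm dropped (4/18): p̄ = 33/78 = 0.4231; X² = 1.7773/0.2441 = 7.28; p = 0.063.
- The change can also go the other way. Responders 7/7/12/5 with dropouts 2/2/5/2, all scored as non-responders: of 20 each, X² = 5.64, p = 0.131; complete records (7/18, 7/18, 12/15, 5/18), X² = 10.13, p = 0.018.

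**3. False-positive rate of the complete-record rule.** Assumptions: the same true response rate in all arms (25–50%), and each non-responder in one arm removed with probability q.

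| q, one arm only | Error rate |
|---|---|
| 5% | 5.0–5.1% |
| 10% | 5.1–5.2% |
| 20% | 5.8–6.0% |
| 30% | 7.2–7.5% |

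With all randomised patients and removals counted as non-responders, the rate is 4.9–5.1%.

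**4. Choosing the rule after seeing the data.** With the same q in every arm, each rule alone holds about 5%. Taking the smaller p gives 5.8–6.1% at q = 10%, 6.3–6.6% at 20% and 6.6–7.0% at 30%.

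**5. Power.** The plan gives shares, not response rates, so I assume overall response of 25, 40 or 50%. Arm rates are then 25/25/40/10, 40/40/64/16 or 50/50/80/20%. Non-responders are removed in the weakest arm only.

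| Analysis | 25% | 40% | 50% |
|---|---|---|---|
| All randomised | 43% | 78% | 94% |
| Complete records, q = 5% | 39% | 75% | 93% |
| Complete records, q = 10% | 37% | 72% | 91% |
| Complete records, q = 30% | 27% | 57% | 82% |

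Unrounded, the loss at q = 5–10% runs from 1.4 points (94.1 to 92.7) to 6.1 points (42.7 to 36.6). With equal 5–10% removal in every arm it is only about 1 to 2 points.

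**The case against.** The strongest reply is that section 8.5 is about missing data and dropout, and that it reads naturally as a general rule followed by a specific one. On that reading LOCF governs every dropout, patients removed for SRRS deterioration stay in as non-responders, and steps 3 and 5 do not apply. This is the likeliest reading and it largely stands. It does not close the gap: complete records as primary with LOCF as an addition also fits the text, and nothing in sections 8.1, 8.3 or 8.5 chooses.

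A reader might infer that the two time points are undefined. They are not: sections 3.2 and 6.1 give baseline and after the last session. A looser reading, which would accept any SRRS taken every 5 sessions, conflicts with those sections and still loses patients who leave before the first such rating.

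A reader might also infer that the primary test is materially inflated. The documents do not support that. At 5–10% removal the effect on error is negligible, and the larger figures need about 30% of one arm's non-responders to be removed. Steps 3 to 5 also treat every removed patient as a non-responder. Section 4.1 allows removal on actigraphy alone or for an adverse reaction, so some removed patients may be SRRS responders, and LOCF would count them as such. The counts in step 2 were chosen: they show that a change of verdict is possible, not that it is likely.

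Finally, one might conclude that every removal must be scored as a failure. The conflict in section 8.5 does not require that; it is a choice of estimand.

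**Conclusion.** The point holds as a conflict between two stated rules: the primary analysis set for the Chi² test and its three interim repeats is not named. It should be fixed, but it is not evidence that the trial's error rate is out of control.

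The size depends on removal rates that the documents do not give. At 5–10% removal in one arm, error stays at 5.0–5.2% and the power loss is about 1 to 6 points if that arm is the weakest. An open choice of the smaller p costs about one percentage point at an equal 10% removal. The 30% case (7.2–7.5% error; power 27/57/82% against 43/78/94%) is an upper end. The stronger claim, that the plan discards its dropouts, is not supported, because LOCF is prescribed for them and largely removes the denominator problem. What remains is that, with 20 per arm, two patients can decide significance under a rule that has not been fixed.

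**What to change.** - Delete the complete-record sentence in section 8.5 as the rule for the primary analysis.
- State that the primary Chi² test, at the interim looks too, uses all randomised patients in their assigned arm. Patients removed for SRRS deterioration count as non-responders, as LOCF already gives. Other missing SRRS follows the plan's LOCF.
- Name complete records and non-responder scoring as sensitivity analyses. Non-responder scoring should not be the default for unrelated loss. If 10% of one arm is lost for reasons unrelated to response, it gives 5.3–5.7% error, against 5.0–5.1% for LOCF (assuming that half of the lost eventual responders already respond). At 30% the figures are 7.7–13.7% against 5.7–6.8%.
- Counting removals for adverse reactions or on actigraphy alone as failures is optional. If it is wanted, fix it in advance and state it as part of the definition of response.
- Reconcile sections 4.1, 7.1 and 9.2 (removal from the study) with section 9.1 (removal from stimulation), since this decides whether an end-of-treatment SRRS exists for these patients.

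The cost is wording, a little more analysis work and slightly lower response rates than with complete records. No new assessments are needed, because SRRS is already repeated every 5 sessions.
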